6.53 Central Nervous System Therapy

In general, no specific CNS therapy will be administered. Patients with CNS disease at initial diagnosis will receive five weekly doses of intrathecal methotrexate (12 mg) both before and after autologous bone marrow transplantation. These patients will then receive monthly doses of intrathecal methotrexate (12 mg) during the first year of remission.

6.54 Supportive Care During Transplant:

On day -6 menstruating females will start provera 10 mg p.o. daily and Nystatin vaginal suppositories 1 b.i.d.. Prophylactic antibiotics: Levofloxacin 500 mg p.o or IV qd until ANC >500, Bactrim DS 1 tablet p.o. b.i.d. will be started at start of conditioning regimen and continued until day - 2.

Prophylaxis for herpes simplex: Patients with positive ab titres for herpes simplex will receive acyclovir 250mg/m² starting day -1 + continue until Day +20 or resolution of mucositis.

Hyperalimentation will be given while patient is unable to eat.

Prophylaxis for veno occlusive disease: Heparin 100 units/kg/day continuous infusion from start of conditioning until ANC >500.

Platelet transfusions will be given to maintain the platelet count > 15,000/ L at all times. Single donor platelets will be used with an attempt to use family members when possible. All platelets will be filtered to remove contaminated leukocytes which may harbor cytomegalovirus (CMV). Packed RBC transfusions will be used to keep the hemoglobin level >8.5 gm/dl. All blood products will be irradiated with 2500 cGy prior to transfusion.

Revised 8/7/00

The greatest risk for autologous BMT is infection. The management of infections in these immunocompromised patients must by necessity be individualized, but the following general approach will be utilized: If a specific infection is documented, patients will be placed on specific antimicrobial agents to treat that infection. For temperatures > 38.5°C without an obvious source in patients with less than 1000 granulocytes/1 cultures of blood and urine will be obtained. Following this, a third generation Cephalosporin will be used as initial empiric antibiotic coverage. For persistent or recurrent fevers an amino glycoside and/or Ancef will be added. Prophylactic intravenous Amphotericin B will be used and the dose can be increased as clinically indicated. If a specific organism or site of infection is identified after starting empiric antibiotic coverage, therapy will be changed as needed.

Revised 8/7/00

While hospitalized, patients will have a daily CBC with platelet count, and basic metabolic panel. Comprehensive metabolic panel plus uric acid, LDH, phosphorous determinations will be performed on Monday, Wednesday, and Friday.

During the first year the patient should be seen monthly and have CBC, Diff., platelets, liver function tests and other tests that are clinically indicated. Bone marrow should be performed at day +100 and then yearly for the first two years after the transplant or when clinically indicated.

6.6 Post Transplant Therapy

After PSCT patients will receive Interleukin-2 once the following criteria are met:

- A. The patient is less than or equal to 100 days after PSCT and meets the following criteria for peripheral blood.
 - i. The patient has an absolute neutrophil count $> 500/\text{mm}^3$ for three days, and
 - ii. The patient has a platelet count that can be supported to $\geq 20,000/\text{mm}^3$ with ≤ one platelet transfusion/day for three days.
- B. Patients must have received no growth factors, corticosteroids, pentoxifylline, or amphotericin-B for at least 72 hours.
- C. Patients must be afebrile and free of active bacterial, viral or fungal infection.
- D. Patients must not be receiving antibacterial, antiviral, or antifungal therapy for fever or a documented infection. Prophylactic antibiotics are allowed.
- E. Patients must have a total bilirubin, SGOT, alkaline phosphatase and creatinine ≤ 1.5 x IULN. These tests must be completed within seven days prior to starting treatment.
- F. Cardiac: EKG with no evidence of active cardiac disease.
- G. Pulmonary: chest x-ray without signs of active pulmonary disease.

These tests must be completed within seven days prior to starting treatment.

- H. Patients must have a KPS of \geq 70%.
- I. Patients must not have mucosal toxicity; not requiring TPN.

6.61 Interleukin-2 (IL-2) Therapy

a). Initiation of IL-2 Therapy

Patients who meet eligibility criteria should begin therapy within three days. Some patients, however, will fail to maintain all eligibility criteria to the initiation of IL-2 therapy. In such cases:

- i) IL-2 therapy should be delayed until the patient again meets all of the criteria for IL-2 therapy at which time IL-2 therapy should begin immediately.
- ii). Patients who have documented relapse of leukemia as determined by peripheral blood or bone marrow findings will be removed from study and not be treated with IL-2.

b). Plan of Treatment

i). IL-2 Preparation

Recombinant human IL-2 (Proleukin) manufactured and provided by Chiron-Cetus Corporation will be used in this study. IL-2 activity will be expressed in International Units (IU).

ii). Outline of IL-2 Treatment Regimen

Treatment Phase	Dose	Route	Days	Notes
Course 1 (IL-2 induction)	9.0×10^6 IU/m ² /24hr	Continuous Infusion	1-4 (total 96hrs)	Requires hospitalization. Begin in AM on Day 1, end in AM on Day 5.
Rest	N/A		5-8	Patient discharged when clinically stable
Course 2 (IL-2 Maintenance)	1.6×10^6 IU/m ² /24hr	Continuous Infusion	9-18	Begin in AM on Day 9, ending in AM on Day 19. Administer as outpatient unless hospitalization is clinically indicated.

c) IL-2 Administration

- i) IL-2 is administered by continuous intravenous infusion (CIV) through a central venous catheter. Interruptions of the infusion should be limited to no more than 20 minutes per 24 hours.
- ii) Induction IL-2 is mixed in 500 cc D5W/day containing 0.1% human serum albumin (HSA) and should be flushed with D5W. The actual volume of each bag containing IL-2 should be determined by the pharmacy in order to calculate the rate to infuse this volume over exactly 24 hours. Failure to do so may result in IL-2 administered for significantly more/less than 96 hours due to overfill/underfill of bags.
- iii) Maintenance IL-2 will be administered by CIV via an ambulatory infusion pump, mixed in D5W containing 0.1% HSA, total volume dependent on the particular pump. During maintenance, the IL-2 solution should be changed mid-course.

Formulation/Reconstitution/Storage

IL-2 (Chiron) is supplied as Glyophilized powder. Each 5 cc vial labeled 1 mg, actually contains 1.3 mg of powder. The vial is reconstituted with 1.2 ml of sterile water for injection producing a final concentration of 18 million International Units/mL (18×10^6 I.V./ml). Diluent should be directed against the side of vial to avoid excess foaming swirl contents gently completely dissolved. Do not

shake. Since vials contain no preservative, reconstituted solution should be used within 8 hours.

Intact vials are stored in the refrigerator (2-8°C) with protection from light. Each vial bears an expiration date.

6.62 Supportive Care During IL-2 Therapy

a) **Intravenous Fluid Administration**

During induction IL-2 therapy, patients retain sodium and free water and generally exhibit and tolerate weight gain of 5-10% of initial body weight. Aggressive sodium and free water restriction may result in hypotension whereas aggressive sodium and fluid administration may result in pulmonary edema and/or ascites. IV fluid therapy during induction IL-2 should be begun as follows, and adjusted according to the patient's subsequent clinical course:

- i) The patient should receive IV hydration with normal saline (NS) at 500 cc/m²/24 hr.
- ii) The patient's total daily IV intake should be limited to \leq 1.5 L/m²/24 hr.

b) **Prophylactic Antibiotics**

IL-2 causes a reversible defect in neutrophil function. Fevers are almost universal during induction IL-2 therapy and usually do not signify infection. However, gram positive, and rarely gram negative, infections occur in 10-25% of patients. These infections can be serious and, therefore, prophylactic antibiotics should be administered as follows (choice of antibiotics may be altered due to a patient history of sensitivity to these medications). Patients are to receive Levaquin 500mg p.o. q.d. while receiving IL-2.

Revised 3/11/02

c) **Ancillary Medications**

To decrease IL-2 toxicity, the following medications are recommended during IL-2 therapy. Alterations may be made based on individual patient factors. **NOTE:** One dose of acetaminophen, diphenhydramine and naprosyn should be administered prior to each dose of IL-2 during the first week. Then for the subsequent weeks acetaminophen should be administered prior to each dose of IL-2. Other medications that could be used for symptom control or prevention are listed below:

- i) **Acetaminophen:** 650 mg PO 30 minutes before first dose of IL-2 is administered and q 4-6 hr as needed for fever.

- ii) **Diphenhydramine:** 50 mg PO 30 minutes before first dose of IL-2 is administered then 25-50 mg PO or IV q 4-6 hours prn for nausea, pruritis.
- iii) **Pepcid:** 20 mg PO or I.V. BID.
- iv) **Meperidine:** 25-50 mg IV q 2 hr or 50 to 150mg po prn for chills
- v) **Prochlorperazine:** 10mg IV or PO q 6 hr prn for nausea.
- vi) **Naproxsyn:** 375 mg PO 30 minutes prior to IL-2, then q 12° for fever/myalgia
- vii) **Contraindicated Medications:** See section 6.64

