6.63 Supportive Care During Maintenance IL-2 Therapy

During IL-2, most patients can be managed on an outpatient basis. Symptoms of malaise, myalgias and anorexia are common and usually peak toward the end of the maintenance course. Fever is uncommon during maintenance (see Section 6.63.d.i.)

- a) IV Fluid Administration is not required unless dictated by inadequate oral intake.
- b) Prophylactic Antibiotics:
 - i) Levofloxacin: 500 mg PO qd, (other antibiotics may be substituted based on the individual patient) while taking IL-2.
- c) Ancillary Medications:

No other ancillary medications to reduce IL-2 toxicity should be routinely administered during maintenance IL-2 therapy.

 - i) Tylenol and Indocin should be avoided since they may mask signs of infection
 - ii) Antiemetics/antidiarrheals/antipuritic agents can be administered as needed on an individual basis.
 - iii) Contraindicated Medications (see Section 6.64)
- d) Toxicity Management:
 - i) Fever is uncommon during maintenance IL-2 and should strongly suggest a concomitant infection. Patients should

not be treated with antipyretics alone until the potential for infection has been evaluated.

- ii) Patients who develop other toxicity(ies) during maintenance IL-2 should be treated according to the guidelines in Section 6.66.

6.64 Contraindicated Medications and Procedures During IL-2 Therapy:

a) **Contraindicated Medications:**

- i) Corticosteroids (including any blood product "pre-meds").
- ii) Pentoxifylline
- iii) IV or IT methotrexate
- iv) IV immunoglobulin
- v) Other cytokines or growth factors

b) **Radiographic Contrast:**

Ten to twenty percent of patients may develop severe "anaphylactoid" reactions with fever, chills and severe hypotension in response to IV contrast (ionic or non-ionic) administered during or within two weeks of completing IL-2 therapy. IV contrast administration (ionic or non-ionic) should, therefore, be avoided unless clinically necessary during these times.

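### Section 6.62(c) calls for acetaminophen before each IL-2 dose after week 1, which can only be maintenance, where 6.63(c) says to avoid it because it may hide infection

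*Combined protocol and SAP*

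**What the plan says.** Section 6.62(c) recommends medications to reduce IL-2 toxicity. Its NOTE asks for acetaminophen, diphenhydramine and naprosyn before each IL-2 dose in the first week, and continues: "Then for the subsequent weeks acetaminophen should be administered prior to each dose of IL-2". The acetaminophen item beneath it reads "650 mg PO 30 minutes before first dose of IL-2 is administered and q 4-6 hr as needed for fever". The list is qualified: "Alterations may be made based on individual patient factors".

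Section 6.61(b)(ii) sets the calendar: induction on Days 1-4, rest on Days 5-8, maintenance on Days 9-18. For maintenance the instruction is "Begin in AM on Day 9, ending in AM on Day 19".

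Section 6.63 covers supportive care in maintenance. Part (c) says "No other ancillary medications to reduce IL-2 toxicity should be routinely administered during maintenance IL-2 therapy" and then "Tylenol and Indocin should be avoided since they may mask signs of infection". Part (d)(i) gives the clinical reasoning: "Fever is uncommon during maintenance IL-2 and should strongly suggest a concomitant infection".

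**The concern.** For the same days of treatment, one section makes giving acetaminophen the default and another makes avoiding it the default. The second gives a safety reason: the drug can hide the sign that maintenance care relies on to detect infection.

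The patients are recent transplant recipients who may start IL-2 with a neutrophil count only just above 500/mm³ (6.6 A). They receive it through a central venous catheter (6.61(c)), and mostly as outpatients during maintenance. Section 6.62(b) itself notes that IL-2 impairs neutrophil function. A site that follows the NOTE literally would give, on a schedule and before any fever is seen, a drug that the maintenance section says to avoid.

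The issue is patient safety and clarity of instruction. Sample size, error rates and the stopping rules are unaffected.

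**Working it through.** The protocol states no figure to reproduce. The check is a calendar comparison followed by simple arithmetic on exposure.

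**Which IL-2 falls after week 1?**

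| Period | Days | IL-2 given (6.61(b)(ii)) |
|---|---|---|
| Week 1 | 1-7 | Induction, Days 1-4, ending the morning of Day 5 |
| Weeks 2-3 | 8-21 | Maintenance only, Days 9-18, ending the morning of Day 19 |

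Could induction run into week 2 after an interruption? No. Under 6.65(b) treatment resumes on the original schedule day, missed doses are not given, and total duration is not extended. All IL-2 covered by the second sentence of the NOTE is therefore maintenance.

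**The two rules for those days**

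| | 6.62(c) NOTE | 6.63(c) |
|---|---|---|
| Acetaminophen (Tylenol) | Give before each IL-2 dose | Avoid |
| Other routine ancillary medication | Not addressed after week 1 | None routinely |
| Stated reason | Reduce IL-2 toxicity | May conceal infection |

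That Tylenol is acetaminophen is ordinary drug naming; the protocol does not say so.

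**How much scheduled exposure?** Maintenance is a continuous infusion, so what counts as a dose is unclear.

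- Duration: morning of Day 9 to morning of Day 19 = 10 days × 24 h = 240 h.
- Infusion start only: 1 dose.
- Start plus one bag change: 2 doses, from 6.61(c)(iii), "During maintenance, the IL-2 solution should be changed mid-course".
- Each daily preparation: 10 doses. This relies on the general dilution text in 4.43.3, which is not specific to maintenance.

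Assume that one dose can mask fever for one dosing interval, 4-6 h, as in 6.62(c)(i). Share of infusion time = doses × hours ÷ 240.

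| Doses | Hours masked per dose | Hours covered | Share of 240 h |
|---|---|---|---|
| 1 | 4 | 4 | 1.7% |
| 2 | 6 | 12 | 5.0% |
| 10 | 4 | 40 | 16.7% |
| 10 | 6 | 60 | 25.0% |

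As-needed doses are left out because they follow a fever already noticed.

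**The case against.** The best defence is that 6.63 is the maintenance section. It repeats the fluids, antibiotics and ancillary-medication layout of 6.62 with maintenance content, and parts (a) and (b) of 6.62 describe induction. A clinician caring for a patient from Day 9 would naturally turn to 6.63. That lowers the chance of error but does not remove the conflict. The heading of 6.62 and the opening of 6.62(c) refer to IL-2 therapy without restriction, no precedence rule is written, and if 6.62(c) applied to induction alone the disputed sentence would apply to nobody.

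The wording is also advisory, and a clinician who withholds acetaminophen complies with both sections. That stands, and it limits the severity. The allowance for individual alterations, however, covers particular patients; it does not reverse the default for all of them.

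Other safeguards are real. Patients must be afebrile and free of active infection before IL-2 starts (6.6 C), levofloxacin continues throughout, and blood counts and chemistry are scheduled on Days 9, 14 and 19 (Appendix V). Section 6.63(d)(i) also bars treating fever with antipyretics alone until infection has been considered. But that rule acts once fever is noticed, so it does not cover pre-dosing.

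The acetaminophen item under the NOTE schedules the drug only before the first IL-2 dose, which makes repeated pre-dosing less likely in practice. It also leaves the section inconsistent within itself.

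Finally, a 2002 revision marker stands just before 6.62(c), and 6.63(c) warns about Indocin, which the 6.62(c) list does not contain. Section 6.62(c) may therefore be the newer text. The marker could equally belong to the antibiotic line above it. The sponsor can confirm its intent, but 6.63 is the section that gives the safety reason.

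**Conclusion.** The conflict is real: on all 10 maintenance days the two sections give opposite defaults for acetaminophen. It should be fixed, although the demonstrated exposure is modest. The maintenance-specific text supports 1-2 scheduled doses per patient, covering about 2-5% of the infusion. The 17-25% range requires each daily preparation to count as a dose. Both ranges rest on the assumption that masking lasts one 4-6 h interval. The documents give no infection rate for the maintenance course, so the effect on recognising infection cannot be estimated.

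**What to change.** In 6.62(c), delete the sentence that carries acetaminophen pre-dosing beyond the first week. In its place, state that from Day 9 ancillary medication, including any antipyretic, is governed by 6.63(c) and (d).

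Leave the existing text for rest Days 5-8 as it is, including the rule in 6.66(g)(iii) on fever persisting after induction. Add no restriction on naproxen beyond what 6.63(c)-(d) already implies.

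The cost is one wording amendment, with no added visits, tests or patients. Some patients may have slightly less symptom relief in maintenance, a trade-off that 6.63(c) already accepts.

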6.63 Supportive Care During Maintenance IL-2 Therapy

During IL-2, most patients can be managed on an outpatient basis. Symptoms of malaise, myalgias and anorexia are common and usually peak toward the end of the maintenance course. Fever is uncommon during maintenance (see Section 6.63.d.i.)

- a) IV Fluid Administration is not required unless dictated by inadequate oral intake.
- b) Prophylactic Antibiotics:
 - i) Levofloxacin: 500 mg PO qd, (other antibiotics may be substituted based on the individual patient) while taking IL-2.
- c) Ancillary Medications:

No other ancillary medications to reduce IL-2 toxicity should be routinely administered during maintenance IL-2 therapy.

 - i) Tylenol and Indocin should be avoided since they may mask signs of infection
 - ii) Antiemetics/antidiarrheals/antipuritic agents can be administered as needed on an individual basis.
 - iii) Contraindicated Medications (see Section 6.64)
- d) Toxicity Management:
 - i) Fever is uncommon during maintenance IL-2 and should strongly suggest a concomitant infection. Patients should

not be treated with antipyretics alone until the potential for infection has been evaluated.

- ii) Patients who develop other toxicity(ies) during maintenance IL-2 should be treated according to the guidelines in Section 6.66.

6.64 Contraindicated Medications and Procedures During IL-2 Therapy:

a) **Contraindicated Medications:**

- i) Corticosteroids (including any blood product "pre-meds").
- ii) Pentoxifylline
- iii) IV or IT methotrexate
- iv) IV immunoglobulin
- v) Other cytokines or growth factors

b) **Radiographic Contrast:**

Ten to twenty percent of patients may develop severe "anaphylactoid" reactions with fever, chills and severe hypotension in response to IV contrast (ionic or non-ionic) administered during or within two weeks of completing IL-2 therapy. IV contrast administration (ionic or non-ionic) should, therefore, be avoided unless clinically necessary during these times.

6.65 Dose Modification during IL-2 Therapy

- a) Treatment with IL-2 is continued until completed or until Grade 3 or 4 toxicity (or Grade 2 neurologic or cardiac toxicity; Grade 4 neutrophils or bilirubin; or platelets $< 10,000/\text{mm}^3$ with transfusions) occurs at which time IL-2 is discontinued until a return to Grade 1 toxicity, at which time IL-2 therapy will be resumed at 50% of the initial dose. If Grade 3 or 4 toxicity, or Grade 2 neurotoxicity or cardiac toxicity, recurs after resumption of the reduced dose of IL-2 then IL-2 is discontinued and not restarted.

- b) Reduction or discontinuation of IL-2 therapy due to toxicity does not alter the IL-2 treatment schema (Section 6.61.b.ii). If temporarily interrupted, IL-2 therapy is resumed according to the day of the original schedule. Any doses missed due to toxicity are not administered, and total duration of therapy is not extended beyond the original plan at initiation of IL-2 therapy.

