- e). Hepatic damage, which can occur in combination with cytoxin or as a single agent and can result in significant hepatic toxicity which, can be fatal.
- f). Temporary hyperpigmentation of the skin and nail bed changes.
- g). Grand mal seizures which can be prevented by the prophylactic administration of Dilantin.

4.4 Interleukin-2 (IL-2) NSC #373364 (Chiron Corporation, Cetus Oncology Unit, Emeryville, California)

4.41 Drug Formulation and Procurement: The recombinant murein IL-2 to be used in this trial is commercially available. It was produced in *E. coli* transfected with the gene for IL-2 isolated from the Jurkat cell line. The IL-2 has been purified to homogeneity and its biological characteristics and *in vivo* effects in animal models have been well studied.

Less than 0.04 mg of endotoxin are present per 1×10^6 units of lyophilized IL-2 in the vial along with 5% mannitol and approximately 50 μ g of SDS. The biological activity of IL-2 is defined as 18 million International Units (IU)/mg protein.

4.42 Drug Toxicity: IL-2 toxicities may include: fever, chills, nausea, vomiting, fatigue, headache, myalgia, arthralgia, weight gain hepatic toxicity, rash, depression of myocardial function, arrhythmias, thrombocytopenia, anemia, hypotension, renal toxicity, diarrhea and transient confusion or psychosis.

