- a. Allow the patients to gain \leq 1-1.5%/day of baseline body weight.
- b. Reserve diuretic therapy for patients with symptomatic interstitial edema (i.e., pulmonary edema, or ascites). Overly aggressive diuresis for asymptomatic patients with weight gain and oliguria will often result in hypotension and worsening of renal dysfunction.
- c. If creatinine increases by $<$ 50% over baseline, reduce indomethacin to q 12 hr.
- d. If creatinine increases by \geq 50% over baseline, discontinue indomethacin.

e) **Hematologic Side Effects – Background:**

IL-2 therapy causes the following hematologic effects.

- i) **Lymphocytosis** as high as 20-50,000/mm³ occurs often and is maximal 24 hours after stopping induction IL-2; lymphopenia occurs during Days 1-4 of induction IL-2.
- ii) **Anemia** occurs often, due to decreased production and destruction RBC's. Most patients will require RBC transfusions during induction IL-2.
- iii) **Neutrophilia and Eosinophilia** occurs often, and is due to secondary release of GM-CSF, IL-5 and IL-3.
- iv) **Thrombocytopenia** occurs often. Platelet counts are lowest on Days 4-9 of IL-2 therapy, and most patients will require more frequent platelet transfusions during this period.

g) **Infectious Complications:**

- i) All patients should receive prophylactic antibiotics during induction IL-2.

- ii) Blood cultures should be drawn at least once per day for temperature spikes.
- iii) Any fever that persists more than 24 hours after induction IL-2 is completed should suggest a secondary infection and **NOT** be ascribed to IL-2 until infection has been ruled out.

h) Gastrointestinal Toxicity:

Nausea, vomiting and diarrhea are common during induction IL-2. Most patients have a limited oral intake during this time. These symptoms usually improve quickly once IL-2 is discontinued.

i) Hepatic Toxicity:

- i) Cholestasis with elevated bilirubin and alkaline phosphatase is common, usually peaks on Day 5-7 and quickly resolves.
- ii) Drugs which are hepatically metabolized may need temporary dose reductions during this period of hepatic dysfunction.

j) Neurologic Toxicity:

- i) Neurologic abnormalities such as lethargy, mild confusion, subtle personality change and memory disturbance occur in some patients receiving narcotics, sedatives or antiemetics concomitantly with IL-2. Patients with these symptoms should have psychoactive drugs reduced or discontinued.

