- ii) In any patient who develops \geq Grade 2 neurologic toxicity, IL-2 will be discontinued immediately and permanently.

7.0 COMPLICATIONS OF THERAPY:

Busulfan: Human toxicity from busulfan includes: a) Severe bone marrow hypoplasia which could be fatal without administration of bone marrow or peripheral blood stem cells. b) Nausea and vomiting which can be decreased by the use of sedation and antiemetics. c) Stomatitis and diarrhea which can be treated symptomatically with fluid replacement and atropine or diphenoxylate Hcl. d) Pulmonary fibrosis characterized by delayed onset of cough, shortness of breath and low grade fever. e) Hepatic damage which can occur in combination with melphalan or as a single agent and can result in significant hepatic toxicity which can be fatal. f) Temporary hyperpigmentation of the skin and nail bed changes. g) Grand mal seizures which can be prevented by the prophylactic administration of dilantin.

Total body irradiation: The short term and long term complications of TBI have been reviewed by others. Most patients will experience nausea and vomiting. This problem will be managed symptomatically and usually resolves within 24 hours of ending therapy. Oral mucositis is expected in virtually all patients. Mouth care will be performed with hydrogen peroxide and clotrimazole. Only toothbrushes will be allowed. Pain will be managed with morphine or dilaudid. All patients should expect permanent sterility. It is probable that most patients will be infertile from previous therapy, but male patients will be offered the option of semen storage before therapy. Temporary alopecia will also be expected in all patients. Long term survivors may develop cataracts within a few years following BMT. These can be managed successfully in the same way as cataracts, unrelated to radiation. Solid tumors have been seen following TBI. Radiation fibrosis of the lung and hypothyroidism are also potential but unlikely complications.

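### Sections 6.65(a) and 6.66(j)(ii) give opposite orders on restarting IL-2 after a first neurologic toxicity of Grade 2 or higher, and no text says which prevails

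*Combined protocol and SAP*

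**What the plan says.** Section 6.65(a) governs dose modification throughout IL-2 therapy. Its triggers are any Grade 3 or 4 toxicity plus some named events, among them "Grade 2 neurologic or cardiac toxicity". After a trigger, "IL-2 is discontinued until a return to Grade 1 toxicity, at which time IL-2 therapy will be resumed at 50% of the initial dose". A second clause deals with a repeat of any severe event and extends to milder neurologic and cardiac ones: "or Grade 2 neurotoxicity or cardiac toxicity, recurs after resumption of the reduced dose of IL-2 then IL-2 is discontinued and not restarted".

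Section 6.66(j)(ii) addresses any patient at or above the same neurologic threshold: "Grade 2 neurologic toxicity, IL-2 will be discontinued immediately and permanently". It is not limited to a recurrence or to one IL-2 course.

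Two cross-references bear on the choice. Section 6.63(d)(ii) reads "Patients who develop other toxicity(ies) during maintenance IL-2 should be treated according to the guidelines in Section 6.66". Section 6.66(b), inside the capillary leak syndrome item, sends dose modification for specific organ toxicities to 6.65.

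Section 6.65(b) fixes the calendar: "Any doses missed due to toxicity are not administered, and total duration of therapy is not extended beyond the original plan". Section 8.1 evaluates the role of IL-2 by whether it can be given and tolerated, and sets no numerical criterion.

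**The concern.** After the same adverse event, one section sends the patient back onto IL-2 at a reduced dose and the other forbids it. This is a safety instruction, and a treating physician may read either section first. More than one centre is involved: 6.4 refers to participating sites, and Appendix IIa gives another hospital's irradiation schema. Two centres could therefore act differently while both follow the protocol.

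The protocol anticipates this kind of toxicity. The IL-2 toxicity list in 4.42 ends with "diarrhea and transient confusion or psychosis", so effects that pass are foreseen. Section 6.66(j)(i) adds that "Neurologic abnormalities such as lethargy, mild confusion, subtle personality change and memory disturbance occur in some patients", meaning those who are also taking narcotics, sedatives or antiemetics, and advises cutting back psychoactive drugs. Neither place gives a grade, a rate or a recovery time.

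For a patient who recovers in time, the IL-2 dose received and whether the course counts as completed depend on the section followed. Both could enter the tolerability summary under 8.1.

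**Working it through.** **Step 1. The two rules side by side, for neurologic toxicity of Grade 2 or higher**

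| Moment | 6.65(a) | 6.66(j)(ii) | Same? |
|---|---|---|---|
| Onset of first event | Stop | Stop | Yes |
| Back to Grade 1 within the schedule | Resume at 50% | Do not resume | No |
| Not back to Grade 1 within the schedule | Nothing further given | Nothing further given | Yes |
| Recurrence on the reduced dose | Permanent stop | Permanent stop (already in force) | Yes |

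The rules differ in one row only.

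**Step 2. Can the text be reconciled?**

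- *Specific over general.* This does not work. Section 6.65(a) names neurologic toxicity in both clauses, and its recurrence clause makes sense only if IL-2 was restarted after a first such event.
- *Cross-references.* Section 6.63(d)(ii) favours 6.66, but for maintenance only. Section 6.66(b) favours 6.65, but sits within the capillary leak item. Neither states precedence.

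**Step 3. Dose at stake per affected patient**

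Inputs, from the regimen table in 6.61(b)(ii), in 10^6 IU/m²:

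- Induction: 9.0 per day on days 1-4, so 9.0 x 4 = 36.
- Rest: days 5-8.
- Maintenance: 1.6 per day on days 9-18, so 1.6 x 10 = 16.
- Planned total: 36 + 16 = 52.

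Missed doses are not made up (6.65(b)).

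Assumptions: the day of return to Grade 1 is not in the documents, so it is varied. The 50% is applied to the dose scheduled for the day, giving 4.5 in induction and 0.8 in maintenance. Taking half of 9.0 as the maintenance rate instead would give 36 + 4.5 x 10 = 81, or 81/52 = 156% of plan. That cannot be meant as a reduction.

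*Event at the end of day 4.* Under 6.66(j)(ii) the patient receives 36, and 36/52 = 69%. Under 6.65(a), with restart on day d, the patient receives 36 + 0.8 x (19 - d).

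| Restart | 6.65(a) total | % of plan | Gap | Gap, % of plan |
|---|---|---|---|---|
| Day 9 | 36 + 8.0 = 44.0 | 85% | 8.0 | 15% |
| Day 14 | 36 + 4.0 = 40.0 | 77% | 4.0 | 8% |
| Day 18 | 36 + 0.8 = 36.8 | 71% | 0.8 | 2% |
| None by day 18 | 36.0 | 69% | 0 | 0% |

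*Event at the end of day 1, restart on day 3 (illustration).* Under 6.66(j)(ii): 9.0. Under 6.65(a): 9.0 + 2 x 4.5 + 10 x 0.8 = 26.0. Gap: 26.0 - 9.0 = 17.0, and 17/52 = 33%.

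The first table is therefore not an upper bound. The gap is larger when the event comes early enough for IL-2 to restart within induction.

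**The case against.** The strongest reply is that the practical difference is small. Both rules stop IL-2 at once. Section 6.65(a) also demands recovery to Grade 1, halves the dose and ends treatment on recurrence. After an event at the end of induction, the restart rate is 0.8 against 9.0 at onset, and 0.8/9.0 is about 9%. Section 6.66(a) describes the toxicity of high-dose IL-2 as dependent on dose and time. This stands as a limit on the risk from re-challenge in maintenance. It does not cover a restart within induction, where the rate would be 4.5, and it does not say which order to follow.

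A second reply is that the documents do not show which rule was intended. This stands. A reader might infer that the permanent stop is the true rule and 6.65(a) a slip. The text does not support that: 6.65(a) names neurotoxicity twice and 6.66(b) points to 6.65, so planned re-challenge is a fair reading.

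A third reply is that 6.63(d)(ii) settles the matter for maintenance. It lends weight to 6.66 there, but leaves in place the explicit neurologic wording of 6.65(a), which covers all IL-2 therapy. It does not reach events that begin in induction.

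A reader might also take 6.66(j)(i) as evidence that these effects resolve. It does not say so, and it ties them to co-medication. Only the word for transience in 4.42 supports that idea.

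**Conclusion.** The conflict is real and stands in current text. For a first neurologic toxicity of Grade 2 or higher that returns to Grade 1 within the 18-day schedule, the two sections cannot both be obeyed. That conclusion rests on the wording alone, and confidence in it is high.

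The size is less certain. The per-patient gap runs from 0 to 15% of planned IL-2 for an event at the end of day 4, and reaches 33% in the day-1 illustration. Both rest on assumed recovery days and on 50% of the scheduled daily dose. The number of patients affected is unknown and may be zero.

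A reader might infer that the trial's efficacy result or its monitoring is compromised. The documents do not support this: DFS, the sample size in 8.2 and the boundaries in 8.4 are unaffected, and 8.1 has no tolerability threshold that the difference could cross. What is touched is patient safety and the descriptive account of IL-2 feasibility and tolerability. It should be fixed because it is a contradictory safety instruction and cheap to correct.

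**What to change.** Make the two sections state one rule. As the safety default, keep the permanent stop:

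- In the hold-and-resume clause of 6.65(a), limit the Grade 3 or 4 trigger to non-neurologic toxicity, and keep cardiac toxicity as the only Grade 2 trigger.
- Make the same change in the recurrence clause.
- Add one sentence: for neurologic toxicity of Grade 2 or higher, IL-2 is stopped permanently, as in 6.66(j)(ii).

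If the principal investigator confirms that re-challenge was intended, leave 6.65(a) as it is and amend 6.66(j)(ii) to match. In either case, notify the participating sites.

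The cost is a few words of text and a notice; sample size, visits and endpoints do not change. The stricter rule has a clinical price: patients with quickly reversible events forgo the remaining half-dose IL-2, in the amounts shown in the working.
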